18. APPENDIX 2 - PROGRAMMING CONSIDERATIONS

All tables, data listings, figures (TLFs), and statistical analyses will be generated using SAS®, Release 9.3 or higher (SAS® Institute Inc., Cary, NC, USA). Computer-generated table, listing and figure output will adhere to the following specifications.

18.1. GENERAL CONSIDERATIONS

- One SAS program can create several outputs.
- One output file can contain several outputs.
- Output files will be delivered in Rich Text Format (RTF) for draft and in PDF format for final.

18.2. TABLE, LISTING, AND FIGURE FORMAT

18.2.1. General

- All TLFs will be produced in landscape format, unless otherwise specified.
- All TLFs will be produced using the Courier New font, size 8
- The data displays for all TLFs will have a 1.5-inch binding margin on top of a landscape oriented page and a minimum 1-inch margin on the other 3 sides.
- Headers and footers for figures will be in Courier New font, size 8.
- Legends will be used for all figures with more than 1 variable, group, or item displayed.
- Tables and listings will be in black and white (no color), unless otherwise specified. Figures will be provided in color.
- Specialized text styles, such as bolding, italics, borders, shading, and superscripted and subscripted text, will not be used in the TLFs, unless otherwise specified. On some occasions, superscripts 1, 2, or 3 may be used (see below).
- Only standard keyboard characters will be used in the TLFs. Special characters, such as non-printable control characters, printer-specific, or font-specific characters, will not be used. Hexadecimal-derived characters will be used, where possible, if they are appropriate to help display math symbols (e.g., μ). Certain subscripts and superscripts (e.g., cm^2) will be employed on a case-by-case basis.
- Mixed case will be used for all titles, footnotes, column headers, and programmer-supplied formats, as appropriate.

18.2.2. Headers

- All output should have the following header at the top left of each page:

Sunovion Pharmaceuticals, Inc.

Protocol SEP360-310
- All output should have Page n of N at the top or bottom right corner of each page. TLFs should be internally paginated in relation to the total length (i.e., the page number should appear sequentially as page n of N, where N is the total number of pages in the table).

18.2.3. Display Titles

- Each TLF should be identified by the designation and a numeral. (i.e., Table 14.1.1). International Conference on Harmonization (ICH) E3 numbering is strongly recommended but sponsor preferences should be obtained prior to final determination. A decimal system (x.y and x.y.z) should be used to identify TLFs with related contents. The title is centered. The analysis population should be identified on the line immediately following the title. The title and table designation are single spaced. A solid line spanning the margins will separate the display titles from the column headers. There will be 1 blank line between the last title and the solid line.

Table x.y.z
First Line of Title
(<Population Name>)

18.2.4. Column Headers

- Column headings should be displayed immediately below the solid line described above in initial upper-case characters.
- In the case of efficacy tables, the variable (or characteristic) column will be on the far left followed by the DB treatment group columns and total column (if applicable). P-values may be presented under the total column or in separate p-value column (if applicable). Within-treatment comparisons may have p-values presented in a row beneath the summary statistics for that treatment.
- For numeric variables, include “unit” in column or row heading when appropriate.

Protocol SEP360-310, Version 0.1

- Analysis set sizes will be presented for each DB treatment group in the column heading as (N=xx) (or in the row headings if applicable). This is distinct from the ‘n’ used for the descriptive statistics representing the number of subjects in the analysis set.
- The order of treatments in the tables and listings will be Placebo first in the case of placebo controlled studies and Active comparators first in the case of active comparator trials, followed by a ‘All’ or ‘Total’ column (if applicable).

18.2.5. Body of the Data Display

18.2.5.1. Table Conventions

- Units will be included where available.
- If the categories of a parameter are ordered, then all categories between the maximum and minimum category should be presented in the table, even if n=0 for all treatment groups in a given category that is between the minimum and maximum level for that parameter. For example, the frequency distribution for symptom severity would appear as:

Severity Rating	N
severe	0
moderate	8
mild	3

Where percentages are presented in these tables, zero percentages will not be presented and so any counts of 0 will be presented as 0 and not as 0 (0%).

- An Unknown or Missing category may be added to any parameter for which information is not available for 1 or more subjects.
- Unless otherwise specified, the estimated mean and median for a set of values should be printed out to 1 more significant digit than the original values, and standard deviations should be printed out to 2 more significant digits than the original values. The minimum and maximum should report the same significant digits as the original values. For example, for systolic blood pressure:

n	XX
Mean	XXX.X
Std Dev	X.XX
Median	XXX.X
Minimum	XXX
Maximum	XXX

- Tabular display of data for medical history, prior / concomitant medications, and all tabular displays of adverse event data should be presented by the body system,

Protocol SEP360-310, Version 0.1

treatment class, or SOC with the highest occurrence in the active treatment group in decreasing order, assuming all terms are coded. Within the body system, drug class and SOC, medical history (by PT), drugs (by ATC code), and adverse events (by preferred term) should be displayed in decreasing order. If incidence for more than 1 term is identical, those terms should then be sorted alphabetically.

- Missing descriptive statistics or p-values which cannot be estimated should be reported as “-” with a corresponding footnote (“- = unknown or not evaluated”), or as “N/A”, with the footnote “N/A = not applicable”, whichever is appropriate.
- The percentage of subjects is normally calculated as a proportion of the number of subjects assessed in the relevant treatment group (or overall) for the analysis set presented. However, careful consideration is required in many instances due to the complicated nature of selecting the denominator, usually the appropriate number of subjects exposed.
- Where a category with a subheading (such as SOC) has to be split over more than one page, output the subheading followed by “(cont)” at the top of each subsequent page. The overall summary statistics for the subheading should only be output on the first relevant page.

18.2.5.2. Listing Conventions

- Listings will be sorted for presentation in order of double-blind treatment groups as noted in [section 6.1](#), subject number, visit/collection day, and visit/collection time.
- Dates will be printed as recorded on CRF.
- All observed time values must be presented as recorded on CRF.
- Units will be included where available.

18.2.5.3. Figure Conventions

- Unless otherwise specified, for all figures, time will be displayed on the X-axis and endpoint (e.g., overall survival) values will be displayed on the Y-axis.

18.2.6. Footnotes

- A solid line spanning the margins will separate the body of the data display from the footnotes.
- All footnotes will be left justified with single-line spacing immediately below the solid line underneath the data display.
- Footnotes should begin with “Note:” if an informational footnote, or 1, 2, 3, or a, b, c etc. if a reference footnote. Each new footnote should start on a new line where possible.

Protocol SEP360-310, Version 0.1

- Footnotes will be used sparingly and must add value to the table, figure, or data listing.
- The last line of the footnote section will be a standard source line that indicates the name of the program used to produce the data display, the listing source (only for table outputs) and the date the output was produced.

Cross-reference: Listing xx.x

Program: Txxxxx.sas

<date>

19. APPENDIX 3 – HANDLING PARTIAL/MISSING DATES

19.1. MEDICATION DATE

For prior and concomitant medications with incomplete dates, the following rules will be used to impute start and/or stop dates for the purposes of determining if a medication is prior or concomitant only.

- For start dates, if day is missing the first of the month will be used. If month is missing January will be used. If the start date is completely missing, the date of first dose will be used. If the stop date is complete and the imputed start date is after the actual stop date, then the start date will be imputed as the stop date.
- For stop dates, if the day is missing then the last day of the month will be used. If the month is missing then December will be used. If the stop date is completely missing then the date of last dose will be used. If the start date is complete and the imputed stop date is earlier than the actual start date, the stop date will be imputed as the start date.

Both prior and concomitant medications are collected on the same CRF page, the following rules will be used to distinguish prior versus concomitant medication:

- Medications with a start date prior to the first date of study drug will be considered prior medications.
- Medications with a start date on or after the first date of study drug will be considered concomitant medications.
- Medications that are ongoing are considered concomitant medications.

19.2. ADVERSE EVENT DATE

If the adverse event start date is partially or completely missing, then the following rules will be used to impute the start date for the purposes of determining the treatment emergence of adverse events. .

- If the start day is missing then the first day of the month will be used.
- If the start month is missing then January will be used.
- If the start date is completely missing then the date of first dose will be used.

Protocol SEP360-310, Version 0.1

- If the end date is complete and the imputed start date is after the end date, then the start date will be imputed as the end date.

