# 11.4. Study Visits and Assessments

#### 11.4.1. Open-label Baseline: Visit 1E (Day 0)

Subjects will be evaluated at the Open-label Baseline Visit to determine their eligibility to enroll in the study. The following study-related procedures will be performed at Open-label Baseline in the following order:

- Obtain informed consent/assent
- Review inclusion/exclusion criteria
- Dispense study drug

The following study-related procedures will be carried over from the core study Week 6 visit and do not need to be performed for the Open-label Baseline visit:

- Medical and psychiatric histories
- Physical and neurological examinations
- Concomitant medications
- Vital signs, height, weight, and BMI
- AEs
- ECG
- Tanner Staging
- C-SSRS, CGI-S, ADHD-RS-IV HV, Conners 3-P, CSHQ
- WFIRS-P
- Clinical laboratories (hematology, chemistry, lipid panel, thyroid panel, sex hormone tests, urinalysis), UDS, and serum pregnancy test for females of child bearing potential
- Breath alcohol test

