5. STUDY ENDPOINTS

5.1. PRIMARY ENDPOINT

The primary endpoint is:

- The incidence of overall AEs (or SAEs), and AEs (or SAEs) leading to discontinuation.

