12.1. ADVERSE EVENTS (AEs)

The summary of AEs (or SAEs) will be limited to TEAEs. A TEAE is any AE (or SAE) occurring on or after the date of the first dose of study drug in the SEP360-310 study. All AEs will be coded using MedDRA version 19.0.

TEAEs will be further divided into:

- 1.) Those events with onset between the date of the first dose of study drug in the SEP360-310 study and 3 days after the last dose of study medication in SEP360-310, inclusive. These will be called on treatment events.
- 2.) Those events with onset more than 3 days after the last dose of study medication in SEP360-310. These will be called post-treatment events.

AEs with preferred terms of “Insomnia”, “Initial insomnia”, “Middle insomnia”, or “Terminal insomnia”, or AEs with Higher Level Term of “Disturbances in initiating and maintaining sleep” will be presented on AE tables in a combined term called “Combined insomnia” with the individual preferred terms within the combined term directly underneath.

All TEAEs will be summarized by SOC and PT. Though only TEAEs will be included in the summary tables, all AEs will be included on the listings (non-TEAEs will be flagged).

An overall summary table of TEAEs by DB treatment will be produced for the following categories:

- Number and percentage of subjects with a TEAE
- Number and percentage of subjects with a treatment-related TEAE
- Number and percentage of subjects with a TEAE leading to discontinuation
- Number and percentage of subjects with a Treatment-related TEAE leading to discontinuation
- Number and percentage of subjects with a serious TEAE
- Number and percentage of subjects with a serious TEAE leading to discontinuation
- Number and percentage of subjects with a treatment-related serious TEAE
- Number and percentage of subjects with a Treatment-related serious TEAE leading to discontinuation
- Number and percentage of subjects with a TEAE leading to death

This overall summary will be repeated for each onset period. For the post-treatment events, the denominators will be the number of subjects in each DB treatment group whose end of study visit was more than 3 days after the last dose date.

Subgroup analyses of the above noted TEAE categories will be produced for the following subgroups (sex, race (categorized as White, Black or African American, Asian, and Other), DB baseline age group (6-9 vs. 10-12 years)).

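### The partial-date rule for adverse events ignores the first-dose date, so a true TEAE with a missing day in the first-dose month is nearly always dropped from the TEAE tables

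*SAP*

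**What the plan says.** SAP 19.2 states that its rules serve to "impute the start date for the purposes of determining the treatment emergence of adverse events". There are three start-date rules:

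- Day missing: "If the start day is missing then the first day of the month will be used".
- Month missing: "If the start month is missing then January will be used".
- Everything missing: "If the start date is completely missing then the date of first dose will be used".

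The one remaining rule compares the imputed start with a complete end date and moves the start back to the end date if it would otherwise fall later. SAP 6.2.3 refers to Appendix 3 and adds no further check.

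SAP 12.1 supplies the test that the imputed date must pass: "A TEAE is any AE (or SAE) occurring on or after the date of the first dose of study drug in the SEP360-310 study". The same section restricts the AE summaries to TEAEs. Other events appear only in the listings, with a flag. The primary endpoint in SAP 5.1 is "The incidence of overall AEs (or SAEs), and AEs (or SAEs) leading to discontinuation".

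Adverse events are also among the items brought forward at the open-label baseline. Protocol 11.4.1 introduces that list with "The following study-related procedures will be carried over from the core study Week 6 visit".

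**The concern.** Only the rule for a completely missing date refers to the first dose. A partial date is pushed to the earliest day it could be, even when the recorded month and year are compatible with onset on open-label drug. The rule is inconsistent with itself. A site that records nothing about onset produces a TEAE (unless a complete end date precedes first dose). A site that correctly records the month of first dose usually produces a non-TEAE.

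This also runs against the SAP's handling of other missing AE data. In section 12.1 a missing severity is taken as severe and a missing relationship as related.

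The error has one direction for true TEAEs: it removes them from the tables behind the primary endpoint. It falls mainly on early onsets, which include the first weeks of exposure for former placebo subjects. Single SOC or preferred-term rows can move more than the overall rate, because a subject leaves the any-TEAE count only when no other TEAE remains.

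**Working it through.** The documents give no figure on this point, so there is none to reproduce. The check applies the rule as written.

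**Inputs from the documents.** The imputation rules in SAP 19.2; the TEAE test in SAP 12.1 (start date on or after first dose); first dose on the morning after the open-label baseline visit (SAP 4.1), so it can fall on any day of the month; follow-up to Day 203 (schedule of assessments); up to 330 subjects (SAP 4.2).

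**Assumptions.** First-dose dates spread evenly over 731 consecutive days (2015 and 2016). Onset 0 to 202 days after first dose, either uniform or exponential with mean 14, 28 or 56 days, truncated at 203 days.

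**Step 1: one case.** First dose on the 15th, true onset on the 20th of the same month, day not recorded. The imputed start is the 1st, which precedes the 15th, so the event is non-TEAE. The same holds for any first dose on days 2 to 31. Only a first dose on the 1st keeps the event. The end-date rule rescues nothing, because it can only move a start earlier.

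**Step 2: share misclassified within the first-dose month, uniform onset.** For each first-dose date, count the days from first dose to month end. Over the 731 dates these total 11,505 days, of which 731 belong to first doses on the 1st.

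Misclassified share = (11,505 − 731) / 11,505 = 93.6%.

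**Step 3: share of all day-missing true TEAEs lost, uniform onset.**

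- Onset in the first-dose month: 11,505 / (731 × 203) = 11,505 / 148,393 = 7.8%.
- Lost: (11,505 − 731) / 148,393 = 7.3%.

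**Step 4: the same enumeration with early-weighted onset.** Weight exp(−k/mean) on day k after first dose, k = 0 to 202.

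| Onset pattern (assumed) | Onset in first-dose month | Of these, classed non-TEAE | Lost among all day-missing TEAEs |
|---|---|---|---|
| Uniform, 203 days | 7.8% | 93.6% | 7.3% |
| Exponential, mean 56 days | 24.2% | 94.2% | 22.8% |
| Exponential, mean 28 days | 40.2% | 94.6% | 38.0% |
| Exponential, mean 14 days | 60.7% | 95.2% | 57.8% |

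The last column is the product of the two before it. Day-missing onsets in later months stay TEAEs.

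**Step 5: day and month both missing.** Onset in the calendar year of first dose is set to 1 January and fails the test unless first dose was on 1 January. That is 364 of 365 first-dose dates, or 99.7%. A site that knows only the year should be rare.

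**Step 6: effect on overall incidence.** Suppose 1%, 2% or 5% of 330 subjects (assumed; not in the documents) have a missing-day event as their only TEAE. The number lost is 330 × rate × (0.073 to 0.578).

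| Assumed rate | Subjects concerned | Subjects lost | Percentage points |
|---|---|---|---|
| 1% | 3.3 | 0.2 to 1.9 | 0.1 to 0.6 |
| 2% | 6.6 | 0.5 to 3.8 | 0.1 to 1.2 |
| 5% | 16.5 | 1.2 to 9.5 | 0.4 to 2.9 |

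**The case against.** The mechanism is hard to dispute; the case against concerns its importance.

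- **Direction.** The percentages are conditional on the event being a true TEAE. In an extension study some partial dates belong to core-study events carried over at baseline, and the present rule correctly keeps those out. This stands as a limit: 93.6% to 95.2% is not the share of all ambiguous records that are misclassified. It does not justify the rule, because carried-over events can be excluded directly.
- **Size.** The 1% to 5% rates have no source in the documents. The 9.5-subject figure combines the highest rate with the most front-loaded curve. Former 2 mg and 4 mg subjects pass over without a break in treatment, and open-label dosing starts at 2 mg/day, so early clustering may be weaker than that curve implies. This stands, and the upper end should be read as a bound under those assumptions.
- **Mitigation.** Visits are closest together in Weeks 1 to 6, so onset dates should be best known there. Data queries can recover missing days. SAEs go on a separate form within 1 business day (Protocol 12.4.1), and SAEs and AEs leading to discontinuation have their own listings. These reduce the number of cases but leave the rule unchanged for those that remain.
- **Completely missing dates.** These are not always TEAEs: a complete end date before first dose already makes them non-TEAE. That is correct, but it is a narrow exception.
- **Cost of the fix.** The SAP describes database carry-over for histories and medications but not for AEs, so the derivation needs specifying. However, Protocol 11.4.1 and footnote a of the schedule show that AE data are duplicated from the core study's Week 6 visit, so the source should be identifiable.

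**Conclusion.** The concern holds. As written, SAP 19.2 classes a true TEAE as non-TEAE whenever the day is missing, onset is in the first-dose month and first dose was not on the 1st. That is 93.6% to 95.2% of such events under the onset patterns examined. The loss among all day-missing true TEAEs depends strongly on the assumed pattern, from 7.3% to 57.8%.

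Confidence is high for the mechanism and its direction. The absolute effect cannot be derived from the documents, because the number of partial dates is not given, and it is probably small. The study is descriptive and affected events remain in the listings, so no test is at stake. Still, the rule biases the primary safety endpoint in the favourable direction and is cheap to correct. It should be fixed before database lock.

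**What to change.** Replace the start-date rules in SAP 19.2 with these steps, applied in order:

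1. If the event was carried over from the core study with onset before first dose, or has a complete end date before the first SEP360-310 dose, classify it as non-TEAE whichever parts of the start date are missing.
2. Otherwise, if the known month and year (or the year alone, when only that is known) equal those of the first SEP360-310 dose, impute the first-dose date.
3. If the known parts are later than first dose, keep the first day of the known month, or 1 January of the known year.
4. If the known parts are earlier, classify as non-TEAE.
5. Keep the first-dose date for a completely missing start date.

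The cost is a few lines of SAP text and one derivation that uses the carry-over source of the AE record. Misclassification of true TEAEs in the first-dose month falls to zero, and TEAE counts may rise slightly. A pre-dose event that is not recognised as carried over, has no complete pre-dose end date and has a partial start date matching first dose would be counted as a TEAE. That residual error is in the conservative direction, in line with how section 12.1 treats missing severity and relationship.
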